Protection against risk (see Parent Protection of Human Subjects for more detail): Our opioid messages are developed with the guidance of pediatric pain and risk communications experts. The intervention poses no more than minimal risk to adolescents or young adults but may instead, offer potential benefit in terms of risk reduction, self-efficacy and pain management competency.

We will minimize the risk for breach of confidentiality of all participants by training of study team members, use of electronic and physical security measures for data capture and storage, and by employing a Certificate of Confidentiality (automatic for NIH funded studies). Unique study identifiers (ID) for each subject will permit linkage between surveys and follow-up data while maintaining the privacy of every participant. ID links between subjects and their data will be kept separately in an encrypted file. Data will only be stored on fire-walled databases which will limit access only to those assigned appropriate permissions.

Routine management will not be altered and we will exclude those who cannot, by nature of their underlying condition be safely prescribed the usual combination of opioids and non-opioids for postoperative pain. We will record all adverse events and will review non-serious AEs

quarterly and serious AEs as they are learned to determine the relationship to study participation and actions needed, if any (see DSMP).

Data and safety monitoring plan (DSMP): Our study specific DSMP provides details of how we will collect, review, evaluate and manage adverse events that may happen as part of routine care or study participation.

Group assignment (same as parent study): Patients will be randomly assigned a priori by computer generated randomization to either the Control Group (i.e., Routine provider written/verbal analgesic instruction) or one of two Intervention Groups: STOMP written (prose) feedback (i.e., Routine provider information plus the STOMP written feedback or our enhanced STOMP Video feedback (i.e., Routine provider information plus STOMP Video feedback).

Outcomes

Aim 1) Opioid risk perceptions, misuse risk perceptions, intentions to medically misuse, non-medically misuse or divert left-over opioids

Aim 2) Persistent opioid use after surgery, left-over opioid retention

Measurements (only modifications from parent grant are described)

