Our sample size is based on our recent findings that 26% of adolescents/young adults indicated a willingness to misuse a prescribed opioid for pain management. We need 426 participants (142/group) to detect a clinically important effect of the STOMP intervention on misuse intention (i.e., decrease to 13%; 95% confidence and 80% power). This sample will be more than sufficient to detect an expected mean difference in opioid misuse risk perception between either intervention group and the control (MD 0.56, SD 1.21; sample needed = 122) and to test for a modest effect of the interventions in a factorial design (estimated eta squared 0.14; sample needed = 147). To allow for 30% loss to follow-up and to account for missing data, we will recruit up to 600 participants.

Table 1. Sequence of study assessments

Measures	Time 0 Baseline (preop)	Time 0.1 (Immediately Post-Session)	Time 1 (7 days)	Time 2 (14 days)	Time 3 (1 month)	Time 4 (3 months)
Demographics	x					
Pain, Analgesic and Misuse History	x					
Pain relief Preference	x			x		
Opioid knowledge/ risk perceptions	x	x		x	x	x
Opioid misuse risk perceptions	x	x		x	x	x
Scenario (situational) decision-making	x			x	x	x
Analgesic self-efficacy	x	x				
Pain interference			x	x	x	x
Opioid left-over disposal				x	x	x

Analgesic use and ADEs			x	x	x	x
Perioperative data	x					
Analgesic refill data				x		

DATA ANALYSES

Generalized estimating equations (GEE) will be used to model both continuous (i.e., negative binomial and Gaussian) and binary outcomes (i.e., binomial) for each aim.^{151,152} All models will include both time-varying measures (e.g., opioid risk perceptions) and time-invariant covariates (e.g., sex, race, etc.) and will use either an independent or exchangeable correlation structure to correct for within subject correlations. Analyses will use Stata's (STATA/SE v.13; STATA Corp., College Station, TX) 'xtgee' option as appropriate. All hypotheses per our conceptual model (Figure 3) will be tested at the 0.05 alpha level. Standardized coefficients and adjusted odds ratios will be computed to determine the relative effect size for each of the key independent variables.

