Missing data: The use of electronic surveys with built-in prompts for incomplete items will reduce the potential for missing responses. Patients will be contacted by phone, text or email (per their preference) to promote ongoing recording of postoperative data and to reduce the potential for missing data and LTF. We have used similar procedures to successfully ensure complete data and minimize loss to follow-up.^{8,25,94,153}

Any remaining missing data on surveys (e.g., assist or PR-Pref) will be examined for randomness and we will impute only partial non-response (e.g., missing 1 to 2 items of PR-Pref or assist) using a horizontal (i.e., per individual) approach. Largely incomplete or total survey non-response will be examined for non-randomness and potential bias (e.g., missing DAST-10). These missing data will not be imputed, however, outcomes will be compared for persons with missing vs. complete data to determine selection bias. We have adjusted our sample size to account for the potential for missing data. We will use pairwise deletion to use the available, complete cases to test our hypotheses.

Aim 1: Using GEE, we will examine the association between the STOMP intervention and the outcomes (risk seriousness perception, and situational opioid decisions). It is hypothesized that, compared to controls, patients who receive the STOMP intervention will have 1) enhanced risk perceptions (continuous measure) and 2) improved opioid decisions (scenario-based). Hypotheses 1 and 2 will be tested using both main and interaction effect models. In the main effects models, STOMP group assignment is our binary independent variable of interest. Time by intervention interaction effect models will be used to examine whether the STOMP group has improved opioid risk perceptions and decisions at the follow-up assessments compared to the control group. It is expected that there will be no difference between the intervention group and control group at baseline. However, significant interaction effect terms should emerge for the intervention group at the follow-up assessments.

Anticipated Problems and Solutions:

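### No outcome, visit or arm contrast is named as primary while every hypothesis is tested at 0.05, although 142 per group was sized for one pairwise comparison of misuse intention

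*Combined protocol and SAP*

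**What the plan says.** The Outcomes section lists five unranked Aim 1 outcomes: "Opioid risk perceptions, misuse risk perceptions, intentions to medically misuse, non-medically misuse or divert left-over opioids". Two more, persistent use and left-over retention, fall under Aim 2. Group assignment describes three groups: control, STOMP written and STOMP video.

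Sample Size Determination rests on one outcome: "We need 426 participants (142/group) to detect a clinically important effect of the STOMP intervention on misuse intention". The control rate is that "26% of adolescents/young adults indicated a willingness to misuse a prescribed opioid for pain management", and the target is given as "decrease to 13%; 95% confidence and 80% power". The same paragraph adds a second calculation, for the "expected mean difference in opioid misuse risk perception between either intervention group and the control (MD 0.56, SD 1.21; sample needed = 122"), and a third for a factorial effect. No visit is attached to any of them.

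Data Analyses sets the threshold: "All hypotheses per our conceptual model (Figure 3) will be tested at the 0.05 alpha level". Its Aim 1 paragraph names two outcome families, risk perception and scenario decisions. It tests both hypotheses with main-effect and time-by-intervention models, and codes STOMP assignment as a binary variable. It expects that "significant interaction effect terms should emerge for the intervention group at the follow-up assessments", without saying which assessments. Table 1 schedules risk perceptions at four post-baseline times and scenario decisions at three.

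No adjustment, testing order, gatekeeping or omnibus test appears.

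**The concern.** The 80% power claim belongs to one outcome and one contrast, but the analysis section does not commit to either. If misuse intention shows nothing, a perception score at one visit, or one arm's interaction term, could become the headline at the same 0.05. These are different claims: a rise in perceived risk right after the session is not a fall in willingness to misuse at three months.

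Three choices stay open even for the outcome that sized the trial:

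- **Scoring.** Under Measurements, opioid decision-making uses four scenarios, with no rule for combining them. The fourth concerns symptom relief when adverse events are present, which is not a misuse intention.
- **Visit.** Decisions are measured at 14 days, 1 month and 3 months.
- **Arms.** The design and the sample size use three groups. The Aim 1 model uses a binary variable.

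**Working it through.** **1. Reproduce the plan's figure.** Inputs from Sample Size Determination: p1 = 0.26, p2 = 0.13, power 80%, alpha 0.05 (two-sided assumed, since sidedness is not stated).

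n per group = (1.960 + 0.842)² × [p1(1 − p1) + p2(1 − p2)] / (p1 − p2)²
= 7.849 × (0.1924 + 0.1131) / 0.0169 = 7.849 × 0.3055 / 0.0169 = 141.9, so 142.

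3 × 142 = 426. Both figures match the plan. The calculation covers one arm against control, on one binary outcome, at one time, with no allowance for a second arm.

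**2. Error rate over the readings the text allows.** For m tests at 0.05 under no effect:

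- independent: 1 − 0.95^m
- common correlation 0.5 (an assumption): the probability that at least one of m equicorrelated standard normal statistics exceeds 1.96 in absolute value

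| Reading | Tests | Correlation 0.5 | Independent |
|---|---|---|---|
| Two outcome families, arms pooled, one test each; or one outcome at one visit, two arms | 2 | 9% | 9.8% |
| Risk perception at 4 times plus decisions at 3 times, arms pooled | 4 + 3 = 7 | 23% | 30% |
| The same 7 by two arms; or 7 listed outcomes by two arms at one visit each | 14 | 35% | 51% |

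With a more structured assumption (0.5 between arms, 0.5 to 0.7 between times, weaker between outcomes), the 7-test figure is 22-26% and the 14-test figure 36-43%. The choice of correlation pattern changes little.

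**3. What a single primary contrast costs in power.** The same variance formula is used, and both STOMP arms are assumed to be at 13%.

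- *Pooled STOMP against control, 284 against 142.* SE = √(0.1924/142 + 0.1131/284) = 0.0419. 0.13/0.0419 − 1.96 = 1.14, so power is about 87%.
- *Fixed sequence.* The first arm comparison keeps 0.05 and the planned 80%. The second is tested at 0.05 only if the first is significant.
- *Splitting alpha, 0.025 each.* n = (2.241 + 0.842)² × 0.3055 / 0.0169 = 171.8, so 172 per group, or 516 in total. At 30% loss this means enrolling 516/0.7 = 737.1, so 738, against 600 planned. At 142 per group, power per comparison would be about 70%.

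**The case against.** The strongest defence is that an order is implied. The sample size is built on misuse intention, and the other outcomes are mentioned only as ones for which that sample is ample. That much stands: misuse intention is the natural primary. But it has no label, visit or scoring rule, and the Aim 1 analysis paragraph puts risk perception first.

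Three stronger readings are tempting, and the documents do not support them.

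- **A count of 42 tests, with an 88% chance of a false positive.** This needs every listed outcome, both arms and every visit to be tested separately. The Aim 1 paragraph pools STOMP into a binary variable and names two outcome families. A main-effect model gives one arm effect per outcome across visits. Aim 2 has no analysis paragraph from which to count tests. The figure is an extrapolation.
- **Any single significant term counts as success.** The sentence that "significant interaction effect terms should emerge for the intervention group at the follow-up assessments" states an expectation, not a decision rule. H1 in the Specific Aims asks for understanding that is sustained, which one isolated visit would not show. The percentages above therefore describe exposure to a selective claim, not a rule the plan adopts.
- **No hierarchy exists anywhere.** The alpha sentence points to Figure 3, which is not in the text available, and the supplement leans on a parent grant that is also not available. A ranking there cannot be excluded. The supplement has its own outcomes and sample size, so it should state the ranking itself.

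**Conclusion.** The point holds as a gap in declaration. The available text leaves the headline claim without a defined primary test, and so without type I error control, although the sponsor has already powered one specific comparison. The size is a range, because the test count is an assumption. It runs from about 9-10% on the narrowest reading, through 23-30% with arms pooled and visits tested separately, to 35-51% if the arms are also separated or all seven outcomes are tested in both arms. Even the narrowest reading exceeds 5%. All figures assume two-sided tests and no true effect, and the lower ends assume correlation 0.5. The point does not require every secondary outcome to be adjusted.

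**What to change.** Add to Data Analyses, before the data are examined:

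1. **Primary outcome.** Misuse intention, scored as one stated binary endpoint from the misuse scenarios under Measurements. Leave out scenario 4.
2. **Visit.** One stated assessment, for example 3 months.
3. **Contrast at 0.05.** Choose one. Either test pooled STOMP against control, which matches the binary variable in the Aim 1 paragraph, or test the two arm-versus-control comparisons in a stated fixed sequence.
4. **Everything else.** Label all other outcomes, visits and interaction terms secondary, and report them with confidence intervals and no confirmatory claim.

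A joint test of arm-by-time terms is a poor substitute as the primary, because 142 per group was not sized for it. As an illustration, an effect giving 80% power on 1 degree of freedom gives about 64% on 3 and 52% on 6.

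The cost is wording only, with no added participants under either option in item 3. Splitting alpha between the arms would not be free, at about 172 per group. Secondary outcomes lose confirmatory status. Pooling does not separate written from video STOMP, and a fixed sequence leaves the second arm formally untested if the first comparison fails.

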- **Analgesic adherence:** Participants will record postoperative analgesics administered, self-reported pain scores (i.e. 0-10 Numeric Rating Scale), and adverse effects the follow-up surveys. Opioids will be converted to oral morphine equivalents, and opioid and non-opioid consumption will be reported as total mg/kg given. Adherence will be reported as the percentage used of the total opioid and non-opioid doses prescribed. The number of left-over doses of opioids will be calculated at discontinuation (amount dispensed minus amount used). We will assess intention to keep left-overs and reasoning at follow-up.
- **Pain interference:** The PROMIS Adult Pain Interference Short Form will also be used to measure how much pain is interfering with participants' activities at 1 and 2 weeks.^{48,49}
- **Adverse side effects:** Participants will document all analgesic-related side effects using the follow-up surveys.⁷ We will also review the clinic notes (6 months) for surgical and analgesic-related calls, return visits to the clinic or hospital, and analgesic refill orders, and persistent pain documentation.

Measurements of Contributing Factors

- **Key biologic and other characteristics of the participant:** Participants will record their demographics including sex and race and ethnicity.
- **Substance Use:** We will use the ASSIST measure for adults as a gross measure of risk factors for substance use disorder.⁵⁰
- **Pain history and opioid familiarity:** History of participant pain, opioid and non-opioid use will be assessed with simple categorical items.^{8,46}
- **Pain relief preference (PR-Pref):** This instrument assesses the participant's desire to provide pain relief relative to their desire to minimize ADE risks. The instrument includes 7 risk–benefit items^{7,8,46} similar to those used to assess the importance patients place on chronic medication benefits versus their concern for adverse effects.¹⁴⁵⁻¹⁴⁷ Agreement with each statement is ranked on a 5 point Likert scale from strongly disagree (-2) to strongly agree (+2), to yield a total score ranging from -12 to +12, where lower numbers indicate a preference for risk avoidance, higher numbers pain relief, and the middle range, indifference or ambivalence.^{145,147} We previously have demonstrated the instrument's internal consistency, construct and predictive validity (higher scores predict parental opioid administration).⁴⁶

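### Aim 1 GEE models have no usable rule for a missing baseline covariate, so participants with a known arm and outcome are dropped from any model containing a covariate they left blank

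*Combined protocol and SAP*

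**What the plan says.** On model content, the Data Analyses section states: "All models will include both time-varying measures (e.g., opioid risk perceptions) and time-invariant covariates (e.g., sex, race, etc". The list is open: sex, race and opioid risk perceptions are the only terms named. Under Measurements of Contributing Factors, sex, race and ethnicity are recorded by the participant, so they can be missing too. The models are to be fitted with Stata's xtgee.

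On missing data, the plan imputes within a person when one or two items of a survey such as PR-Pref or ASSIST are blank. For larger gaps it says: "Largely incomplete or total survey non-response will be examined for non-randomness and potential bias (e.g., missing DAST-10". Those gaps are not filled; outcomes are instead compared between people with missing and complete data. The paragraph closes with: "We will use pairwise deletion to use the available, complete cases to test our hypotheses".

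The example given for an unanswered survey is a substance-use questionnaire, which is not among the listed outcomes. The Contributing Factors section names a different instrument: "We will use the ASSIST measure for adults as a gross measure of risk factors for substance use disorder".

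Table 1 schedules "Pain relief Preference" (PR-Pref) at baseline and 14 days only. Scenario decisions are collected at baseline, 14 days, 1 month and 3 months. Risk perceptions are collected at those times and also immediately after the session.

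**The concern.** Pairwise deletion works where a statistic is built from pairs of variables, such as a covariance matrix. A GEE fitted row by row is not built that way: a row contributes only if the outcome and every covariate in the model are present. The closing sentence of the Missing data paragraph therefore amounts to dropping incomplete rows. A participant can be randomised, followed up and have a recorded outcome, and still leave the arm comparison because one adjustment variable is blank.

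That loss is avoidable. Arm is randomised, so a covariate measured before the intervention can be filled without reference to arm and flagged as missing, and the participant stays in. What is at stake is precision. The sample is sized close to 80% power for one STOMP arm against control, and recruitment to 600 covers the 426 needed only approximately if the full 30% is lost.

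A second exposure depends on a choice the plan leaves open. If PR-Pref were entered as a repeated measure, the visits at which it is not collected would drop out of the model.

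**Working it through.** **Inputs (Sample Size Determination).** Control rate: "26% of adolescents/young adults indicated a willingness to misuse a prescribed opioid for pain management". Target: "decrease to 13%; 95% confidence and 80% power". Size: "We need 426 participants (142/group"). Recruitment is up to 600, allowing 30% for loss and missing data. Alpha 0.05 is taken as two-sided. The share of participants with a known outcome but a missing covariate is not given; 10% and 20% are assumed for illustration.

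**Reproducing the plan's figure.** With unpooled variance, n per group = (1.960 + 0.842)² × (0.26×0.74 + 0.13×0.87) / 0.13² = 7.849 × 0.3055 / 0.0169 = 141.9, so 142 per group and 426 in all. This matches.

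**Recruitment allowance.** 426 / 0.70 = 609, against 600 stated. If the full 30% is lost, 600 × 0.70 = 420, or 140 per arm.

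**Power formulas.** Let SE = √(0.1924/n_c + 0.1131/n_t).

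- Unpooled: power = Φ(0.13/SE − 1.960).
- Pooled: power = Φ((0.13 − 1.960·SE₀)/SE), with SE₀ = √(p̄(1−p̄)(1/n_c + 1/n_t)).
- p̄ = (0.26 + 0.13)/2 = 0.195 for one STOMP arm, and (0.26 + 2×0.13)/3 = 0.173 for both STOMP arms combined (n_t = 2n_c).

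Example: at 126 per arm, one STOMP arm, SE = √(0.3055/126) = 0.0492; 0.13/0.0492 − 1.960 = 0.68; Φ = 75.2%.

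| Assumed covariate loss | Per arm | One STOMP arm vs control (unpooled / pooled) | Both STOMP arms vs control (unpooled / pooled) |
|---|---|---|---|
| 0% | 140 | 79.5% / 78.7% | 86.9% / 89.6% |
| 10% | 140 × 0.90 = 126 | 75.2% / 74.3% | 83.3% / 86.5% |
| 20% | 140 × 0.80 = 112 | 70.2% / 69.2% | 78.7% / 82.5% |

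**Dropping versus filling.** A logistic simulation (2,000 runs, one STOMP arm, assuming that higher-risk youths skip more often) gave power of 74% and 66% when incomplete rows were dropped at about 10% and 20% missing. With mean fill plus an indicator it gave 78% and 79%. The arm effect showed no material bias. These results depend on the assumed skip pattern.

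**PR-Pref, if entered as a repeated covariate.** Set against Table 1, with 600 participants and complete follow-up:

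- Scenario decisions have 4 time points, of which 2 (baseline and 14 days) have PR-Pref. That leaves 1,200 of 2,400 rows, with none at 1 or 3 months.
- Risk perceptions have 5 time points, of which 2 have PR-Pref. That leaves 1,200 of 3,000 rows; the immediate post-session rows go as well.

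The time-by-intervention terms at 1 and 3 months could not then be estimated. Entered as its Time 0 value, PR-Pref removes no visit by design.

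**The case against.** The strongest reply is that the exposure may be small.

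- Only sex, race and opioid risk perceptions are named as model terms. ASSIST, DAST-10 and PR-Pref are never placed in a model. A reader might infer that every adjusted STOMP comparison loses participants through an unanswered substance-use survey. The documents do not support that, because the loss occurs only in models that contain the blank covariate. This stands.
- A reader might also infer that the 1- and 3-month data will be lost through PR-Pref. Nothing in the plan says PR-Pref enters as time-varying. The one time-varying example, opioid risk perceptions, is collected at every scenario-decision visit. The PR-Pref loss is conditional only.
- The starting point of 140 per arm is the worst case within the allowance, which is itself meant to cover missing data. Specific Aims reports current loss to follow-up below 15%. At 15%, 600 × 0.85 / 3 = 170 per arm. A further 10% or 20% leaves 153 or 136, and by the formulas above one-arm power is 82-83% or about 78%. This stands as a limit on the size.
- The analysis text treats STOMP assignment as a binary variable. Read as both arms combined, power stays near or above 80%. The sample-size text, however, also speaks of either intervention group against control, so both readings matter.
- Survey prompts, filling of one or two items, and the comparison of missing with complete responders are real mitigations. The comparison can reveal selection, but it returns nobody to the model.
- Someone who skips the whole Time 0 survey also lacks the baseline outcome and, in a STOMP arm, that session's messages. A known outcome with only a covariate missing is therefore a narrower pattern than total non-response.

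What remains is that the plan itself foresees unanswered surveys, puts covariates in all models, and has no rule that keeps these participants in.

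**Conclusion.** The point holds in a limited form. As written, a randomised participant with known arm and outcome is dropped from any xtgee model that includes a baseline covariate they did not answer, and the pairwise-deletion sentence cannot prevent it. Under assumed covariate loss of 10% or 20% from 140 per arm, the cost is about 4 or 9 percentage points of power for one STOMP arm against control, and about 3-4 or 7-8 points for both arms combined. It is smaller in absolute terms if follow-up loss stays below the 30% allowed. The size depends on a non-response rate the documents do not give and on a covariate list they leave open.

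The demonstrated harm is lost precision. A reader might infer that the arm effect is biased, or that those lost are the highest-risk youths. The documents give no evidence on who skips, and the simulation, which assumed that pattern, found no material bias. The ASSIST and DAST-10 mismatch is a clerical side point. The change is worth making because it costs almost nothing.

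**What to change.** For the Aim 1 randomised arm-comparison models, replace the pairwise-deletion sentence with wording such as:

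> *Adjustment covariates are Time 0 values. A missing Time 0 covariate is set to the overall arm-blind mean with a missing indicator (or, if categorical, given its own category). No participant with an observed outcome is excluded for a missing covariate.*

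Bring the general statement about time-varying measures in all models into line with this, so that it does not override the Aim 1 rule. Leave the Aim 2 mediation models free to use post-baseline risk perceptions, which that hypothesis needs. If PR-Pref is used in Aim 1, state that its Time 0 value is entered. Mean fill with an indicator is one acceptable method; another prespecified method that keeps these participants would also serve.

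As housekeeping, name one substance-use instrument throughout and show it in Table 1 at Time 0.

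The cost is SAP wording, a few extra model terms and a few lines of code, with no new data. Making good the same assumed loss by recruitment would need 426 / (0.70 × 0.90) = 677 or 426 / (0.70 × 0.80) = 761 participants, against the planned ceiling of 600.
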